4.2 Secondary outcomes

Willingness to dispense naloxone: Seven items measure willingness to dispense naloxone; four items came from the Nielsen et al. (2016) naloxone attitudes survey and two items from the Wilson et al. (2016) HOPE measure^{26,27}. A seventh item was created to reflect initiating a conversation about naloxone. At baseline, immediately post-intervention, and three months post-intervention, pharmacists indicate how willing they are to engage in activities such as "proactively identify customers who are candidates for naloxone" and "dispense naloxone to patients and caregivers."

Response options range from 1 = “Not at all willing” to 4 = “Very willing.” Items are averaged to create a mean willingness score, with higher scores indicating more willingness to dispense naloxone.

Naloxone counseling self-efficacy: There are no validated instruments to measure pharmacists’ naloxone counseling self-efficacy. Thus, we referred to the qualitative literature on pharmacists’ barriers to dispensing naloxone^{11,15-17,26,28,29} and identified factors that could impact counseling self-efficacy. On the baseline, immediate post-intervention, and three-month post-intervention surveys, pharmacists rate their confidence to engage in seven naloxone communication tasks, including engaging in naloxone counseling when the pharmacy is busy and discussing naloxone in a way that does not offend customers. Response options range from 1 = “Not at all confident” to 4 = “Very confident.” Items are averaged to create a mean self-efficacy score (range = 1 to 4), with higher scores indicating greater naloxone counseling self-efficacy.

Quality of naloxone counseling: SPs assess pharmacists’ quality of naloxone counseling at baseline and four weeks post-intervention. During a phone interaction with the pharmacist, SPs use a validated observation guide with six items to rate the pharmacist’s quality of communication on a 5-point scale (1 = lowest score and 5 = highest score). These items specifically assess satisfaction with communication (e.g., listened carefully, showed respect, and actively engaged with their case). This method for measuring impressions of communication has been used previously to assess the effect of training on pharmacists’ ability to communicate about antidepressants²¹.

Three separate SPs rate each pharmacist both pre-intervention and post-intervention. The three ratings are averaged to create summary scores for quality of communication before and after training (range = 1 to 5), with higher scores indicating higher quality of communication.

In addition to the six items, the observation guide asks if the pharmacist encouraged or made a personal recommendation for naloxone, what term the pharmacist used to describe naloxone’s use (e.g., overdose, opioid emergency), and which analogy or comparison was used to describe naloxone (e.g., EpiPen, fire extinguisher).

4.3 Other measures

Naloxone knowledge: Six multiple-choice questions and two true/false questions based on the content of the naloxone training modules assess participants’ naloxone knowledge. Correct answers are totaled to create a summary score (range = 0 to 6), with higher scores indicating greater naloxone knowledge.

Attitudes toward dispensing naloxone: Eight items from the Wilson et al. (2016) HOPE measure assess participants’ attitudes toward naloxone²⁷. Items relate to attitudes toward substance abuse (e.g., “I believe chemical dependency is a disease”) and naloxone (e.g., “Giving patients naloxone for overdose reversal will cause them to use more drugs”). Response options range from 1 = “Strongly disagree” to 4 = “Strongly agree”. Items are reverse scored as necessary and averaged to create a mean score (range = 1 to 4), with higher scores indicating more negative attitudes toward naloxone.

Barriers to dispensing naloxone: This construct is assessed using items from the HOPE measure²⁷. Pharmacists report how much of a concern 10 attitudinal and environmental barriers are for dispensing naloxone, including not wanting to insult the patient and lack of time to counsel. Response options range from 1 = “Not at all concerned” to 5 = “Extremely concerned.” Items are averaged to create a mean score (range = 1 to 5), with higher scores indicating more barriers to dispensing naloxone.

Previous naloxone training: At baseline, pharmacists indicate whether they have ever received naloxone training (yes/no) and on the three-month post-intervention survey whether they have received any naloxone training in addition to the training completed as part of the study (yes/no).

Pharmacist characteristics: At baseline, pharmacists report their age, gender, race, ethnicity, how long they have worked in pharmacy practice and at their current pharmacy, and whether they have previously dispensed naloxone (yes/no).

Pharmacy characteristics: At baseline, pharmacists report the number of pharmacists and technicians who are typically at the pharmacy at one time, as well as the estimated daily prescription volume at their pharmacy.

Social desirability bias: The validated short version of the Marlowe-Crowne Social Desirability Scale, Cronbach alpha = 0.65³⁰, assesses pharmacists’ social desirability bias. From 10 statements such as “I’m always willing to admit when I make a mistake” and “I never resent being asked to return a favor”, respondents select statements that are true for them (coded as 1). Unchecked, or “false” statements, are coded as 0. Items are summed so that scores range from 0 to 10, with higher values indicating greater social desirability bias.

5. STATISTICAL CONSIDERATIONS

Characteristics of pharmacies and pharmacists will be presented by treatment group. Unadjusted statistical comparisons using two sample t-tests and chi-square tests will be made between treatment groups (control vs. intervention group). Generalized estimating equations, (i.e., the GEE method), will be used to analyze the effects of the intervention on the primary and secondary outcome variables, while accounting for the fact that pharmacists are nested within pharmacies.

5.1 Primary outcome

The GEE method will be used to detect a significant difference in our primary outcome variable of frequency of naloxone dispensing. Specifically, we will evaluate change in naloxone dispensing from the 3 months pre-intervention to the 3 months post-intervention. Our multivariable model will be nested by pharmacy and will include several covariates, including the county’s opioid prescribing rate, pharmacy rurality, average daily script fill rate, and demographic characteristics of the pharmacist. Alpha will be set at 0.05.

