Efficacy Evaluations	
Primary outcome: change in naloxone dispensing rates is measured by comparing pharmacy records of naloxone dispensed in the 3 months prior to study participation to number of naloxone dispensed in the 3 months after study completion
 
Secondary outcomes:
 
• Willingness – 7 items measure willingness to dispense naloxone. Pharmacists rate their willingness to engage in each item from 1= “Not at all willing” to 4 = “Very willing.”• Self-efficacy – factors were identified that could impact counseling self-efficacy. On the study surveys, pharmacists rate their confidence to engage in 7 naloxone communication tasks. Response options range from 1 = “Not at all confident” to 4 = “Very confident.”• Quality of naloxone counseling – SPs use a validated observation guide with 6 items to rate the pharmacist’s quality of communication on a 5-point scale (1 = lowest score and 5 = highest score).
Statistical And Analytic Plan	Linear regression using GEE will be used to assess the effect of the intervention on naloxone dispensing rates (primary outcome) after adjusting for any imbalances between the treatment groups. Similar models will be used to assess the effect of the intervention on each secondary outcome.
DATA AND SAFETY MONITORING PLAN	The study PI will evaluate data collected by secret shoppers and through surveys. The PI will also meet weekly with her project director and monthly with the research team to discuss data collection, potential data quality issues if they arise, and study progress. Also, the DSMB will provide an independent and unbiased review of the study’s ongoing progress.

BACKGROUND AND RATIONALE

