4. STUDY EVALUATIONS AND MEASUREMENTS

4.1 Primary outcome

Our primary outcome is change in naloxone dispensing rates measured by comparing pharmacy records of naloxone dispensed in the three months prior to study participation to number of naloxone dispensed in the three months after study completion (Table 2). The grocery store pharmacy chain has agreed to provide us with these naloxone dispensing rates from each of the participating pharmacies at the conclusion of the study. We hypothesize that pharmacies in the experimental group will dispense more naloxone in the three months post-intervention compared to pharmacies in the control group.

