5.2 Secondary outcomes

We will also conduct similar GEE models as the one described above to assess if the intervention improves our secondary outcomes of willingness to dispense naloxone, naloxone counseling self-efficacy, and quality of naloxone counseling.

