5.3 Sample size and power

Pharmacies in this grocery store chain dispense naloxone once for every 250 opioid prescriptions, on average. With 60 pharmacists, 30 per treatment arm, we have at least 80% power at the 0.05 significance level to detect an increase in naloxone dispensing to 1 for every 100 opioid prescriptions dispensed, assuming a standard deviation of 0.008 (2 in 250 or 0.8 in 100) and depending on the intraclass (within pharmacy) correlation. In other words, we expect the intervention to increase the naloxone dispensing rate from 1 in 250 (0.4%) to 1 in 100 (1%), an increase of 0.6%. So, the sample size is based on a mean difference of 0.6%.

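### The primary analysis of change in dispensing does not prespecify the pharmacy's own pre-period naloxone rate as a covariate, although that rate is already part of the outcome

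*Combined protocol and SAP*

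**What the plan says.** Section 4.1 sets the outcome: "Our primary outcome is change in naloxone dispensing rates measured by comparing pharmacy records", three months before against three months after. Section 5.1 repeats that "we will evaluate change in naloxone dispensing from the 3 months pre-intervention to the 3 months post-intervention", using GEE nested by pharmacy. The covariates it names are the county's "opioid prescribing rate, pharmacy rurality, average daily script fill rate, and demographic characteristics of the pharmacist". The list is introduced as non-exhaustive, and pre-period naloxone dispensing is not on it.

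The analytic plan in the synopsis specifies linear regression with GEE "after adjusting for any imbalances between the treatment groups". It names no variable and gives no rule for what counts as an imbalance.

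For the secondary outcomes, Section 5.2 says only "We will also conduct similar GEE models as the one described above". Baseline values exist for all three: Section 4.2 says of willingness that "At baseline, immediately post-intervention, and three months post-intervention, pharmacists indicate how willing they are", self-efficacy follows the same schedule, and counselling quality is rated before and after training. Table 2 confirms the baseline measurements.

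Section 5.3 uses an SD of 0.008. It does not say whether this is the SD of a rate in one period or of the change, and it gives no pre-post correlation.

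**The concern.** A pharmacy's earlier naloxone dispensing is the most direct measure of its prior behaviour, and the matching in Section 2.2 did not use it: pairs were formed on county opioid prescribing rate and rurality. Chance differences between arms in baseline dispensing are therefore not controlled by the design.

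Two things follow. First, an unadjusted change score gives the baseline value a fixed coefficient of one, which is generally not the most precise choice. With 60 pharmacists in at most 60 pharmacies, lost precision matters. Second, the plan leaves it to be decided later whether baseline enters the model. Under Section 4.1 the chain supplies the dispensing rates at the end of the study, so the decision could be made with the outcome data in hand, after an imbalance has been seen.

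No bias in the planned estimate is alleged.

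**Working it through.** **Inputs from Section 5.3:** 30 pharmacists per arm, difference 0.010 − 0.004 = 0.006, SD 0.008, alpha 0.05 (taken as two-sided). **Assumed:** pre-post correlation rho from 0.3 to 0.8, and 30 independent units per arm with no clustering.

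**The plan's own figure.** The standardised difference is 0.006/0.008 = 0.75. A two-sample t-test with 30 per arm (58 df) has 81.5% power, and the normal approximation gives 82.8%. The stated figure of at least 80% is reproduced, with little to spare.

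**Variance.** With SD s in both periods:
- change score: 2s²(1 − rho)
- baseline-adjusted: s²(1 − rho²)
- ratio, change to adjusted: 2/(1 + rho)

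**Power, equal variances** (noncentral t; 58 df for change, 57 for adjusted). Reading A takes 0.008 as the SD of a single-period rate, so the standardised differences are 0.75/√(2(1 − rho)) and 0.75/√(1 − rho²). Reading B takes it as the SD of change, so they are 0.75 and 0.75/√((1 + rho)/2).

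| rho | Variance ratio | A: change | A: adjusted | B: change | B: adjusted |
|---|---|---|---|---|---|
| 0.3 | 1.54 | 67.5% | 84.9% | 81.5% | 94.3% |
| 0.5 | 1.33 | 81.5% | 90.9% | 81.5% | 90.9% |
| 0.7 | 1.18 | 95.8% | 97.9% | 81.5% | 87.2% |
| 0.8 | 1.11 | 99.5% | 99.7% | 81.5% | 85.3% |

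**Power, unequal variances** (reading A). An intervention that raises a low rate may also raise its spread. Let the treated post-period SD be k × 0.008. The variances of change are 2s²(1 − rho) in the control arm and s²(1 + k² − 2·rho·k) in the treated arm. With a common slope b = rho(1 + k)/2, the adjusted variances are s²(1 + b² − 2b·rho) and s²(k² + b² − 2b·rho·k).

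| rho | k = 1.5: ratio | change | adjusted | k = 2: ratio | change | adjusted |
|---|---|---|---|---|---|---|
| 0.3 | 1.26 | 55.0% | 64.9% | 1.13 | 42.5% | 47.0% |
| 0.5 | 1.11 | 68.3% | 72.9% | 1.03 | 52.4% | 53.7% |
| 0.7 | 1.02 | 86.3% | 86.9% | 1.00 | 67.5% | 67.6% |
| 0.8 | 1.00 | 95.1% | 95.1% | 1.04 | 77.7% | 79.2% |

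**Effect of a chance imbalance** (reading A, equal variances). The standard error of the baseline difference between arms is 0.008 × √(2/30) = 0.0021. Given a baseline difference D, the change-score estimate shifts by −(1 − rho)D. At rho = 0.5 and D = 0.002 the shift is −0.001, or 17% of the 0.006 target. This shift averages to zero over randomisations, but it is present in any one trial.

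**Choice of outcome.** Once baseline is a covariate in a linear model, using the post-period rate or the change gives the same arm coefficient and standard error. On simulated data with 60 units both gave 0.6815 (SE 0.2178). Adjustment therefore does not require redefining the outcome.

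**The case against.** The change score is valid, the documents call the trial a pilot, and the stated power is reproduced without adjustment if 0.008 is the SD of change. The open covariate list already allows baseline to be added. All of this is true, and it limits the point to precision and prespecification. But allowing a covariate does not prespecify it, and the synopsis rule depends on the data.

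The gain rests on an assumed rho and may be close to zero. This also stands. The largest equal-variance gain needs rho of 0.3, reading A and 30 independent units per arm. Equal variances are doubtful for a rate expected to rise 2.5-fold. In the scenarios tabulated, however, adjustment costs essentially nothing.

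Section 5.1 could mean a repeated-measures GEE with an arm-by-time term, in which the pre-period value is an outcome row. The plan does not say. With complete data and an unconstrained arm-by-time term, that model estimates the same difference in mean change, so it is no more efficient.

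Dispensing is recorded per pharmacy and both pharmacists in a store may enrol, so 30 independent units per arm is the best case. With 15 pharmacies per arm, reading B and rho 0.5, power is 50.9% for change and 62.8% adjusted. Adjustment still helps, but it does not resolve that separate problem.

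**Conclusion.** The concern holds. The plan analyses change and does not commit to adjusting for the pharmacy's own baseline rate, so whether to adjust is left open until the data are available. With 30 independent units per arm and rho from 0.3 to 0.8, prespecified adjustment adds about 0 to 17 percentage points of power if variances are equal, and about 0 to 10 if the treated post-period SD is 1.5 or 2 times baseline. The size depends on a correlation the documents do not give; the gap in prespecification does not. The change should be made, but the planned estimate is not invalid without it.

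**What to change.** - **Section 5.1 and the synopsis analytic plan, in the same words:** name the pharmacy's naloxone dispensing rate in the three months before participation as a prespecified covariate, included whether or not the arms differ on it. State the model form: one record per analysed unit, with either change or the post-period rate as the outcome. Keeping change agrees with Section 4.1.
- **Section 5.2:** include each secondary outcome's own baseline score as a covariate. For willingness and self-efficacy this applies at both the immediate and three-month time points; for counselling quality, at the single post-training observation.
- **Section 5.3, for clarity:** say whether 0.008 is the SD of the rate or of its change, and state the pre-post correlation assumed.

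The cost is wording in the SAP sections and the synopsis, and one degree of freedom per model. No extra data are needed: the chain must supply the pre-period rate to form the primary outcome, and Table 2 already schedules the secondary baselines.

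### The stated 80% power counts 60 pharmacists, but pharmacies are randomised and supply the primary outcome, so power rests on a number of stores that the plan does not give

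*Combined protocol and SAP*

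**What the plan says.** - **Randomisation (section 2.2).** The 62 pharmacies are matched in pairs, and one member of each pair goes to each arm, so there are 31 stores per arm.
- **Outcome data (section 4.1).** "The grocery store pharmacy chain has agreed to provide us with these naloxone dispensing rates from each of the participating pharmacies". The hypothesis there is also about stores: "pharmacies in the experimental group will dispense more naloxone in the three months post-intervention compared to pharmacies in the control group". Nothing in the document attributes dispensing to an individual pharmacist. The synopsis objective and section 1, however, word the aim for pharmacists.
- **Enrolment (section 2.4).** Each store has two full-time pharmacists and both may join. The target is 60 of 124. No number of participating stores is planned.
- **Analysis (sections 5 and 5.1).** GEE is used for primary and secondary outcomes alike, "accounting for the fact that pharmacists are nested within pharmacies". For the primary outcome, "Our multivariable model will be nested by pharmacy and will include several covariates", including "demographic characteristics of the pharmacist".
- **Power (section 5.3).** The baseline rate belongs to stores: "Pharmacies in this grocery store chain dispense naloxone once for every 250 opioid prescriptions, on average". The sample size belongs to people: "With 60 pharmacists, 30 per treatment arm, we have at least 80% power at the 0.05 significance level". The claim is qualified as "depending on the intraclass (within pharmacy) correlation", with no value given.

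**The concern.** For the primary outcome, two participants in one store are not two sources of information. They share the store's dispensing record, so the within-pharmacy correlation that section 5.3 leaves open is at or near 1, and the effective sample size is close to the number of distinct stores. The plan neither states that number nor controls it.

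The plan also does not say how a two-participant store enters the model: as one row or two, with whose demographics, and with what weight. Two analysts could follow sections 5 and 5.1 faithfully, one weighting stores equally and the other by participants, and report different primary estimates. At stake are whether the power statement can be relied on and whether the primary estimate is fully defined in advance.

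**Working it through.** **Inputs.** From section 5.3: difference 0.006 (0.4% to 1.0%), SD 0.008, 30 per arm, alpha 0.05. My assumptions: a two-sided test; 0.008 is the SD between stores of the analysed change; no gain from covariates or from the matched pairs.

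**1. The plan's own figure.** For n independent units per arm, the standard error is 0.008 × √(2/n) and the noncentrality is 0.006 divided by it. With n = 30: SE = 0.00207, noncentrality 2.90, 58 degrees of freedom, power 81.5% (82.8% by the normal approximation). The claim of at least 80% therefore reproduces with 30 independent units per arm.

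**2. How many stores to expect.** Suppose 60 of the 124 pharmacists enrol at random (an assumption).
- The chance that both pharmacists of a given store enrol is (60 × 59)/(124 × 123) = 0.232. Over 62 stores this gives 14.4 stores with two participants.
- Distinct stores: 60 − 14.4 = 45.6, or about 23 per arm. As a whole-number mix per arm, take 7 stores with two participants and 16 with one.

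**3. Power by number of distinct stores.** Same formula, with n = stores per arm:

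| Stores per arm | Power (t-test) |
|---|---|
| 30 (every participant from a different store) | 82% |
| 29 | 80% |
| 23 (expected under random enrolment) | 70% |
| 20 | 64% |
| 15 (every store has two participants) | 51% |

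So 80% needs 29 of the 31 stores in each arm. With 30 participants, that leaves room for one two-participant store per arm.

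**4. Does the correlation have to be exactly 1?** No. At the 7 + 16 mix, the design effect with participants weighted equally is 1 + (44/30 − 1) × ICC = 1 + 0.467 × ICC, where 44 = 7 × 2² + 16 × 1². Power of 80% needs an effective n of 28.9, so the ICC may be at most (30/28.9 − 1)/0.467, about 0.08.

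**5. What could restore 80% at 23 stores per arm.**
- *Covariates.* If they explain a share R² of the variance, the SD becomes 0.008 × √(1 − R²). Power reaches 80% at R² of about 0.21.
- *Meaning of 0.008.* If it is the SD of one period's rate, the SD of the change is 0.008 × √(2(1 − ρ)), with ρ the pre-post correlation. Power is 56% at ρ = 0.3, 70% at 0.5 and 89.5% at 0.7.

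**6. Cost of weighting by participants.** Under working independence, a two-participant store counts double. At the 7 + 16 mix the effective number of stores per arm is 30²/44 = 20.5, and power is about 65%, against 70% with one record per store. This assumes the same effect whether one or both pharmacists are trained.

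**The case against.** **Clustering is not ignored.** The GEE is clustered by pharmacy, and section 5.3 makes its power conditional on the within-pharmacy correlation. This stands in part. A reader might infer that repeated store values inflate the type I error, but the documents do not support that: a robust variance clustered on pharmacy prevents automatic pseudo-replication. The caveat in 5.3 does not rescue the figure, though, because for a shared store record the correlation is not an open quantity.

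**The two values in a store need not be identical.** Section 4.1 ties the windows to study participation, pharmacists enrol individually (2.3), and each is invited to train after their own simulated-patient calls (3.2). Two colleagues may therefore have different three-month windows. This stands, so the correlation is at or near 1 rather than exactly 1. Step 4 shows that the power conclusion does not need exact equality.

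**The text does not compel a pharmacist-level model.** Nesting by pharmacy could also describe one pre and one post record per store. That is possible, but the pharmacist demographics and section 5 point the other way, and the ambiguity itself needs resolving.

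**Equal store weighting is not automatically right.** If the effect grows with the number of pharmacists trained, the two weightings estimate different quantities. For illustration only, assume effects of 0.3 points with one trained and 0.6 with both. The store-weighted effect at the 7 + 16 mix is (16 × 0.3 + 7 × 0.6)/23 = 0.39 points; the participant-weighted effect is (16 × 0.3 + 14 × 0.6)/30 = 0.44. This stands. The choice is one of estimand and should be declared; neither weighting is shown to be biased.

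**It is a pilot, and the shortfall is conditional.** Both are true. The plan nevertheless names a primary outcome, an alpha and a power figure, and the figure should match the unit that carries the information.

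**Conclusion.** The point holds in a limited form. On the inputs of section 5.3, read as in the working, at least 80% is supported only if almost every participant comes from a different store (29 or more per arm). At the roughly 23 stores per arm expected under random enrolment, power is about 70%; if every store supplied two participants, it would be about 51%.

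A reader might go further and call the trial underpowered. The documents do not show this. The store count is unknown, random enrolment is my assumption, a covariate R² of about 0.21 would restore 80% at 23 stores per arm, and the meaning of 0.008 alone moves power there between 56% and 89.5% over the pre-post correlations tried.

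The undefined handling of two-participant stores leaves the primary estimate open to the analyst's choice and, under participant weighting, costs some precision. This should be corrected, but it does not invalidate the design.

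**What to change.** **Section 5.1.**
- Analyse the primary outcome with one record per participating pharmacy: the change in dispensing rate from the three months before to the three months after.
- Pre-specify one anchor date per store where two pharmacists take part. State the denominator of the rate: 5.3 uses opioid prescriptions, while 4.1 mixes rates with counts. Reconcile the later window, which 4.1 starts at study completion and 5.1 at the intervention.
- Regress on arm, county opioid prescribing rate, rurality and script volume (averaged where two pharmacists report it), with t-based inference. If pharmacist demographics are kept, use store averages.
- State that the primary effect weights stores equally, and report the number of trained pharmacists per store.

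**Sections 5 and 5.2.** Keep the pharmacist-level GEE clustered by pharmacy for the secondary outcomes, which are measured on pharmacists.

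**Section 5.3.** Replace the single power claim with power by number of participating pharmacies, for example 15, 20, 23 and 30 per arm. Say whether 0.008 is the SD of one period's rate, of the change, or of the residual after covariates.

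**Synopsis and sections 1 and 4.1.** Word the primary objective and hypothesis consistently for pharmacies.

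**Cost.** Wording only; no new data. The price is a less favourable stated power if many stores supply two participants.

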2.4 Study Population

The recruitment goal is 60 pharmacists. Each of the 62 pharmacies employs two full-time pharmacists, both of whom can participate. Thus, participants for the RCT (N = 60) will be recruited from a total sample of 124 pharmacists. Eligible pharmacists must meet the following criteria: 1) be age 18 years or older, 2) speak English, 3) work as a full-time pharmacist at one of the participating 62 rural grocery store chain pharmacies. In addition, individuals who are a floater, or non-staff, pharmacist are ineligible.

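### The GEE tests on 30 to 60 pharmacies name no variance estimator, reference distribution or small-sample correction; the usual uncorrected test would have a type I error of about 6.5–11%, not 5%

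*Combined protocol and SAP*

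**What the plan says.** Section 5 states that GEE "will be used to analyze the effects of the intervention on the primary and secondary outcome variables", with clustering by pharmacy. Section 5.1 adds "Our multivariable model will be nested by pharmacy and will include several covariates". It names the county opioid prescribing rate, rurality, daily script volume and an unlisted set of pharmacist demographics, and closes with "Alpha will be set at 0.05". Section 5.2 says "We will also conduct similar GEE models as the one described above" for willingness, self-efficacy and counselling quality. The synopsis calls the primary model a linear regression fitted by GEE, adjusted for imbalances between the groups.

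Section 2.4 says "Each of the 62 pharmacies employs two full-time pharmacists, both of whom can participate", and the recruitment goal is 60 pharmacists. The number of pharmacies in the analysis is therefore not fixed.

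The document does not state the variance estimator, the working correlation, the reference distribution, any small-sample correction, or the exact covariate list.

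**The concern.** GEE inference is commonly reported with the sandwich variance and a normal cut-off. Both rest on having many clusters relative to the number of fitted parameters. With few clusters, the fitted model follows the data too closely, the residuals are too small, and the sandwich variance built from them is biased downward. The normal cut-off also ignores the uncertainty in that variance.

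This trial has 30 to 60 clusters and an adjusted model. An analyst who runs GEE in its ordinary form would probably reject a true null more often than the 5% in Section 5.1, and the 95% intervals would be too narrow. Because the choice is left open, it could also be made after the data are seen.

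**Working it through.** **1. The plan's own figure.** Section 5.3 gives "With 60 pharmacists, 30 per treatment arm, we have at least 80% power at the 0.05 significance level", with a difference of 0.006 and an SD of 0.008. Sidedness is not stated; two-sided is assumed.

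- Standard error = 0.008 × √(2/30) = 0.002066.
- 0.006 / 0.002066 = 2.905.
- Power = Φ(2.905 − 1.960) = 82.8%. The noncentral t gives 81.5%.

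The figure reproduces with no design effect. Section 5.3 does qualify it as "depending on the intraclass (within pharmacy) correlation", but gives no value. The claim assumes that the test holds its 5% level.

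**2. Clusters.** At one or two pharmacists per store, 60 pharmacists come from 30 to 60 pharmacies. If 60 of the 124 volunteer at random, the expected number is 62 × (1 − (64/124)²) = 45.5.

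**3. Parameters.** Intercept, arm and the three named covariates make 5. Section 4.3 lists age, gender, race and ethnicity. Adding all four, with race and ethnicity binary, makes 9. This count is a reading of the plan, not a statement in it.

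**4. Estimators.** Let A = Σ XᵢᵀVᵢ⁻¹Xᵢ, with eᵢ the residuals of pharmacy i and Hᵢ its leverage block.

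- Uncorrected sandwich: A⁻¹ (Σ XᵢᵀVᵢ⁻¹eᵢeᵢᵀVᵢ⁻¹Xᵢ) A⁻¹.
- Kauermann-Carroll: replace eᵢ by (I − Hᵢ)^(−1/2) eᵢ.
- Mancl-DeRouen: replace eᵢ by (I − Hᵢ)⁻¹ eᵢ.

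**5. Simulation under the null.** Each setting has 60 pharmacists, one outcome per pharmacist, and 4,000 or 6,000 replicates. The Monte Carlo standard error near 8% is √(0.08 × 0.92 / 4000) = 0.43 points. Assumed within-pharmacy correlations run from 0 to 1, because the documents give none. Some runs randomised the 62 stores in 31 pairs and used an independence working correlation. Others randomised without pairs and used an exchangeable working correlation fixed at its true value (capped at 0.95).

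Type I error of the uncorrected sandwich with a normal reference, normal outcomes:

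| Pharmacies | 5 parameters | 9 parameters |
|---|---|---|
| 60 | 6.4–6.6% | 8.0–8.1% |
| 45 | 7.5–8.8% | 7.0–9.5% |
| 30–31 | 8.2–8.9% | 8.8–11.2% |

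A further set of runs gave 7.0–9.9% with pharmacy covariates only and 7.7–11.2% with the four demographics added. With a strongly skewed outcome, about 45 pharmacies and 9 parameters, the result was 7.3–7.8%. Taken together, the ranges are about 6.5–9.9% and about 7–11%.

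**6. Alternatives in the same kinds of setting.**

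| Method | Type I error |
|---|---|
| Uncorrected sandwich, t reference only | 5.8–9.2% |
| Kauermann-Carroll, t on pharmacies minus parameters | about 5–6% normal, about 4–5% skewed (3.7–3.9% in the strongly skewed case) |
| Mancl-DeRouen, t | about 3–4% |
| Model-based errors, correct working correlation | 5.0–6.0% |
| Model-based errors, independence working correlation, within-pharmacy correlation near 1 | 10.8–12.4% at 45 pharmacies, 18.6–18.8% at 31 |

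Changing the reference distribution alone is not enough; the variance correction does most of the work.

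**The case against.** The strongest reply is that the documents never say the uncorrected sandwich will be used. Model-based errors with a correct working correlation give 5–6%, and a corrected sandwich gives less. Both fit the text. A reader might infer that the true type I error of this plan is 7–11%. The documents do not support that, because the figure holds only if the uncorrected test is chosen. The reply does not remove the point, however. Model-based errors are safe only if the working correlation is right, and the plan names none. Section 4.1 says dispensing rates come from each participating pharmacy. If two colleagues share one store rate, their correlation is near 1, and an independence working model with model-based errors does worse than the sandwich.

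Second, seven covariates is not a stated count, and the synopsis wording could mean fewer. This stands, but with county and pharmacy covariates only the error is still about 6.5–9.9%.

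Third, the 10–11% end needs almost every participating store to enrol both pharmacists. At about 45 pharmacies the range is 7–10%. In the strongly skewed setting, arguably closest to the primary outcome, it is 7.3–7.8%. This also stands.

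Fourth, willingness and self-efficacy are surveyed at three time points (Section 4.2), and no simulation modelled that. The figures should not be carried over to those two outcomes without a further check.

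Finally, this is a pilot. A reader might infer that a positive result could not be interpreted at all. An excess of a few percentage points calls for caution and a prespecified method; it does not show that.

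**Conclusion.** The point holds in conditional form. With 30 to 60 pharmacies and several covariates, the plan leaves open the choices that decide whether its 5% level is met, and the most usual form of the test would miss it. Under that form, type I error for a single change score is about 6.5–9.9% without demographics and about 7–11% with all four. The omission and the direction of the error are firm. The exact size is less so: it rests on assumed within-pharmacy correlations, covariate distributions and outcome shapes, and on the number of pharmacies that take part.

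**What to change.** In Sections 5.1 and 5.2, state that inference uses the Kauermann-Carroll bias-corrected sandwich variance, with a t reference on (number of pharmacies minus number of model parameters) degrees of freedom. Mancl-DeRouen with t is a valid alternative but conservative, at about 3–4%. The covariate list should be fixed in the same place, since the degrees of freedom depend on it.

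The cost is one sentence in each section and a software option, with slightly wider intervals and slightly lower power. With 9 parameters, the critical value rises from 1.960 to 2.008 at 60 pharmacies (51 df), 2.028 at 45 (36 df) and 2.080 at 30 (21 df). That alone widens intervals by about 2%, 3% and 6%; the variance correction adds to it. The planned power of 81.5–82.8% before clustering leaves little slack, so it should be recomputed under the chosen method.

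Leaving pharmacist demographics out of the primary model would reduce the inflation somewhat, but that is an optional modelling choice and does not replace the correction.
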